The current study explores using tVNS as a potential method to alleviate barriers to establishing a habit of mindfulness practice. In mindfulness interventions it is not uncommon for participants to report an initial escalation of anxiety and distress as they directly engage with negative thoughts. While accepting, decentering, and deriving meaning from these negative reactions is an important feature of the psychotherapeutic process in mindfulness interventions, they can also lead to disengagement or drop out from the intervention. Similarly, difficulty learning the skill of meditation is also common and can contribute to participant dropout. tVNS may exert an anxiolytic effect through effects on limbic structures and activation of the parasympathetic nervous system. Moreover, tVNS increases positive affect (i.e. calm) and has been linked to improved interoceptive awareness, which are two other potential psychological mediators of mindfulness interventions. Thus, these two separate treatment approaches appear complementary, yet there are no published trials using them in combination. **The proposed study will enable us to evaluate the utility of this combined treatment approach in enhancing college student sleep and mental health, with potentially broader impacts for clinical populations.**

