Though digital mindfulness interventions offer many potential sleep and mental health benefits for college students, rates of adherence and sustained use of mindfulness apps have been low. Thus, more research needs to examine facilitators to the uptake and sustainability of mindfulness practice, as well as complementary treatment methods that can boost the perceived effectiveness of mindfulness practice. The current study explores tVNS as one such complementary treatment. tVNS is a safe, non-invasive form of vagus nerve stimulation (FDA-approved for the treatment resistant depression and epilepsy). tVNS targets the auricular branch of the vagus nerve through stimulation at sites of the external ear, such as the inner tragus. It has been shown to affect vagally mediated components of the limbic system that are critical to sleep and mood via activation of the nucleus of the solitary tract (NTS). Moreover, tVNS has been shown to increase parasympathetic tone, which can have a beneficial effect on both sleep and mood. Stimulation of the vagus nerve has been associated with reductions in daytime sleepiness, decreased sleep latency, greater slow wave sleep, and longitudinal improvements in self-reported sleep quality in clinical and preclinical studies. tVNS has also been associated with improvements in anxiety and depressive symptoms. Thus, tVNS may be a convenient means to improve sleep and mental health outcomes among college students engaging in mindfulness practice, although this potential has not yet been empirically tested. The current study will evaluate the feasibility, acceptability, and efficacy of this novel combined treatment approach relative to mindfulness-only and control conditions.

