#### **Analysis Plan.**

- To analyze feasibility data, we will qualitatively examine rates of recruitment and drop out/attrition and compare them to prior research. Quantitatively, to examine whether dropout is selective, participants who completed the study will be compared to participants who dropped out on group via chi-square independence test. To analyze acceptability data, outcomes regarding tolerance and acceptability will be compared between the groups via

ANOVA. In addition, we will perform thematic analysis of participant responses to open-ended questions about feasibility and acceptability.

- To examine trajectory of sleep and mental health/well-being over time, multilevel modeling (MLM) analyses will be conducted using unrestricted full information maximum likelihood in R via the “lme4” package. Separate models will be conducted using each sleep and mental health/well-being outcome measure as a dependent variable. Linear and quadratic time trends will be estimated, and intervention group will be included as a moderator. To examine adherence, the number of minutes participants spend engaged with the app or tVNS device per week will be averaged. Then, an MLM will be conducted using average weekly engagement as the dependent variable and time (linear and quadratic) and group as predictors. Retention rates between intervention groups will be compared using an independent samples t-test.

**Nerve Stimulation.** The auricular branch of the vagus nerve projects to the brainstem and is accessible via electrical stimulation through surface electrodes. Stimulation produces vagus sensory evoked potentials not induced with off-target stimulation.

**Earpiece Placement:** All subjects will be instructed to place the Soterix device earpiece on their left ear such that the stimulation electrode is positioned over the inner tragus and the return electrode is positioned just anterior to the tragus to minimize off-target stimulation per local pilot protocol (see Figure 2). Subjects will demonstrate their ability to set up the stimulator—including earpiece placement—and text the picture of the electrode placement with their faces occluded, similar to Figure 2. Research assistants will also provide a link with an instructional video that participants can refer to in order to ensure they have properly placed their electrodes. Participants will be asked to send a photo of their electrode placement for each stimulation session via SMS.

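### The engagement model names no group-by-time term, so as written it cannot separate a constant gap in minutes from better-sustained practice.

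*Combined protocol and SAP*

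**What the plan says.** The Analysis Plan (section 6.6) describes two kinds of multilevel model in one bullet.

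- Sleep and mental health outcomes: "Linear and quadratic time trends will be estimated, and intervention group will be included as a moderator".
- Engagement: first "the number of minutes participants spend engaged with the app or tVNS device per week will be averaged", and then "an MLM will be conducted using average weekly engagement as the dependent variable and time (linear and quadratic) and group as predictors". The text does not say whether the averaging is within each week or across weeks.

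Two other between-arm comparisons touch on adherence, and both concern leaving the study: "participants who completed the study will be compared to participants who dropped out on group via chi-square independence test", and "Retention rates between intervention groups will be compared using an independent samples t-test".

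On motivation, the Abstract (section 3) says that the study "explores using tVNS as a potential method to alleviate barriers to establishing a habit of mindfulness practice", and the Background (section 4) notes that "rates of adherence and sustained use of mindfulness apps have been low". Specific Aims (section 5) adds another reason, greater efficacy through synergy between tVNS and mindfulness. Section 6.2 and Table 1 place stimulation in the first 2 of the 4 intervention weeks, at the same time as app practice, with 20 participants per arm.

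**The concern.** Where the plan wants arms to differ in their course over time, it says so with the word moderator. For engagement it lists time and group side by side. The natural reading is an additive model, in which every arm rises or falls by the same amount each week and group only shifts the level.

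Sustained practice is a statement about the course over time. An arm that starts level and fades more slowly, and an arm that is simply higher throughout, can produce the same group coefficient. The retention and dropout tests do not help, because a participant can stay in the study and stop practising. At stake is an effect size that the trial could supply from data it already collects: how the trajectory of practice differs between tVNS and sham.

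The averaging step adds an ambiguity. If minutes are averaged across all weeks, each participant has one value and there is no time trend left to fit.

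**Working it through.** The plan gives no power figure, SD, alpha or effect size for engagement, so there is nothing of its own to reproduce. From the documents: 4 arms of 20 (4 × 20 = 80), 4 weeks, and the model terms quoted above. The weekly profiles and SDs, two-sided alpha of 0.05 and complete data are assumptions.

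**1. What can be estimated.** The check is the rank of the fixed-effects design matrix (intercept, time, time squared, group).

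| Data and model | Two arms: columns / rank | Four arms: columns / rank |
|---|---|---|
| One average per person, no interaction | 4 / 2 | 6 / 4 |
| One value per person-week, no interaction | 4 / 4 | 6 / 6 |
| One value per person-week, with group-by-time and group-by-time-squared | 6 / 6 | 12 / 12 |

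With one average per person the time terms cannot be estimated. With weekly values the listed model can be fitted, but its curves are parallel. Adding the interactions keeps full rank.

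**2. What the additive model reports.** Least-squares fits to illustrative mean profiles (minutes in weeks 1 to 4):

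| Arm 1 | Arm 2 | Group effect, additive model | Linear slope difference, interaction model |
|---|---|---|---|
| 55, 50, 45, 40 | 55, 45, 35, 25 | 47.5 − 40 = 7.5 | −5 − (−10) = 5 |
| 50, 45, 40, 35 | 42.5, 37.5, 32.5, 27.5 | 42.5 − 35 = 7.5 | −5 − (−5) = 0 |
| 40, 40, 40, 40 | 55, 45, 35, 25 | 40 − 40 = 0 | 0 − (−10) = 10 |

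The first two rows are different findings with the same group effect. The third is an extreme case in which the group effect vanishes.

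**3. Precision after the change.** Assume SD 14 minutes between persons and 14 within person. With weeks coded −1.5, −0.5, 0.5, 1.5, the sum of squares is 5, so the SD of a person's fitted slope is √(τ² + 14²/5), where τ is the SD of true slopes. The standard error of the arm difference is that SD × √(2/20). Power is for a two-sample t-test with 38 degrees of freedom.

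| τ (min/week) | SD of fitted slope | Power, difference 5 min/week | Power, difference 10 min/week |
|---|---|---|---|
| 0 | √39.2 = 6.26 | 69% | 99.8% |
| 5 | √64.2 = 8.01 | 49% | 97% |
| 8 | √103.2 = 10.16 | 33% | 86% |

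**4. What the additive group term can still detect.** The SD of a person's 4-week mean is √(14² + 14²/4) = 15.65. If arms start level and diverge by 10 minutes per week, the weekly gaps are 0, 10, 20, 30, averaging 15, and the group test has about 84% power. At 5 minutes per week the average gap is 7.5 and power is about 31%.

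**5. A weeks 3–4 contrast as an alternative.** For profiles 55, 53, 51, 49 against 70, 58, 46, 34, the weeks 3–4 means are 50 and 40. The SD of a two-week mean is √(14² + 14²/2) = 17.15, and power for the 10-minute difference is about 44%. This is also a difference in level, so a constant gap would produce it too.

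**The case against.** The strongest reply has four parts.

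- **The text is silent, not restrictive.** Listing time and group as predictors does not exclude an interaction. This stands: the additive form is inferred from the wording and from the contrast with the preceding model. But an interaction that is not named is not pre-specified.
- **The averaging remark has a sensible reading.** A multilevel model with linear and quadratic time only makes sense with one value per person per week. This also stands. A reader might infer that the model cannot be fitted at all, but that follows only from the less natural reading, averaging across weeks.
- **No numbered aim or hypothesis compares persistence between arms.** Research question 1.1 asks about consistent engagement over 4 weeks, and 3.1 about adequate adherence over 2 weeks. The comparative tVNS hypotheses, 4.1 and 4.2, concern sleep and mood, where group is already a moderator. This limits the weight of the point. It does not remove it, because the Abstract and Background both present sustained practice as part of the case for the study.
- **The additive model is not blind.** A reader might infer that a tVNS effect on practice could not be seen at all. Step 4 of the working shows otherwise: if arms start level and diverge, the group term moves. It vanishes only when profiles cross so that their means match. What remains is that a non-zero group effect cannot be attributed to level or to persistence.

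**Conclusion.** The point holds as a gap in specification. As written, the engagement model can report which arm practised more on average, but not whether any arm sustained practice better. That rests on reading the listed predictors as the full set of terms, which the contrast with the outcome models supports but does not prove.

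It would go too far to say that the plan fails to test the reason for adding tVNS. Habit formation is one stated reason and synergistic efficacy is another. It would also be wrong to promise a well-powered test once the term is added. Power near 100% arises only with a slope difference as large as 10 minutes per week and little variation in slope between persons; at 5 minutes per week it is about 33% to 69%. All of these power figures depend on assumed SDs and complete data. The gain is an estimable contrast with a confidence interval, which suits a study that sets out to produce effect sizes.

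**What to change.** In the Analysis Plan:

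1. Define engagement as one value per participant per week, and remove or define the averaging step.
2. Add group-by-time and group-by-time-squared to the engagement model, matching the outcome models.
3. Report the tVNS versus sham difference in trajectory with a 95% CI, labelled as an effect-size estimate and not a confirmatory test. App minutes in weeks 3–4 by arm may be added as a supplementary description.
4. Analyse app minutes separately from device minutes. The device is used together with the app and only in weeks 1–2, so a combined measure could count the same minutes twice or build a week-3 drop into the stimulation arms.
5. State how minutes on the control task enter the model, if at all.

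The cost is wording, two more fixed effects per arm contrast, and limited precision at 20 per arm. Time spent in the app is already captured through the pre-assigned accounts described under Mindfulness Mobile App, so no visit, procedure or sample size changes.

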## 6. Research Plan

**6.1 Study timetable and logistics.** The study will consist of an intake-training session and a 4-week intervention phase. Participants will complete brief weekly online surveys during the intervention phase and a follow-up online survey 4-weeks after the end of the intervention period. Face-to-face interaction with subjects will take place at the University of Florida McKnight Brain Institute (MBI) during the intake-training visit, the return of study equipment, and the distribution of participant payment

**Figure 1** Visualization of the study protocol and timeline.

**6.2 Experimental design.** As participants are scheduled for intake visits, they will be assigned to either a tVNS group (tVNS + mindfulness or sham + mindfulness) or a non-tVNS group (mindfulness only or control) by the research coordinator based on practical considerations (i.e. tVNS device availability) to expedite study completion. Within each of these groups, participants will be randomized via alternating order to either the active or control condition (in other words, once a participant is assigned to a tVNS group, they will then be randomized to either the tVNS + mindfulness or sham + mindfulness group). This process will repeat until each group has the target number of participants.

In the initial visit, a research assistant will review the appropriate informed consent form. During this process, participants assigned to a stimulation group (tVNS + mindfulness or sham + mindfulness) will be told that they have been randomized to receive one of two different types of noninvasive vagal nerve stimulation, that we think one of the conditions may be more effective, and that they have a 50/50 chance of being in that group. For participants randomized to the non-stimulation groups (mindfulness only or control), they will be told that they have been randomly assigned to use one of two mobile app interventions, that we think one of the interventions may be more effective, and that they have a 50/50 chance of being in that group. After providing written informed consent, participants will complete a brief health questionnaire as part of our inclusion/exclusion screening (see section 6.5). If participants screen out after signing the informed consent, the session will end, and any data collected will be kept in a locked filing cabinet.

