**Stimulation Device:** We will use the Soterix Medical RELIfit-Tragus transcutaneous electrical nerve stimulation devices. For details, see “Device type” in my.irb. Stimulus pulses will be alternating in polarity to reduce tissue irritation and will be delivered at 20Hz, 200  $\mu$ s pulse width, within the range of published stimulus parameters.

**Calibration:** Participants will undergo calibration during the intake-training visit. Prior to calibration, participants will be informed that the stimulation intensity will be slowly increased until they report any discomfort and then reduced to a comfortable level for the remainder of the study. Individual sensitivity to tVNS stimulation will then be evaluated with a structured stepped-ramp protocol, with a brief pause at each step during which the participant will be asked what the stimulus felt like to them and if they experienced any discomfort. The stimulation intensity will then be set to 80% of the discomfort threshold for the active tVNS group and near to 0% (just enough to keep device on) of the discomfort threshold for the sham stimulation group. If the participant reports irritation with stimulation during this ramp up procedure (which can last ~15 minutes), electrode adhesion will be checked (if there is poor contact, it can affect the sensation) and stimulation intensity will be reduced if necessary (any change will be documented). If the participant further indicates discomfort, stimulation will be discontinued. If the patient evidence dizziness/lightheadedness or if a comfortable level of stimulation is not achievable at calibration, the participant will be removed from the study (this will be documented).

**Blinding:** Participants will be blinded to condition and told that, after calibration, the stimulus intensity will be set to below the calibration (discomfort threshold) level and that they may not feel the stimulation once reduced. We have used this form of psychological sham approach in

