the past. Participants will be provided with a maximum of 14 blinding codes that correspond with the appropriate stimulation parameters and intensity depending on their group assignment. These blinding codes must be entered into the tVNS device in order for stimulation to be administered. They are one-time use only, meaning that participants will not be able to administer tVNS more frequently than instructed in the study protocol. Moreover, participants will be told that these blinding codes correspond to stimulation parameters/intensity that is calibrated to them only, and that they are not safe to be used on other people (e.g., friends, roommates). The picture of earpiece placement that participants send with each stimulation session should act as a further control against participants allowing others to use the stimulation device. The blinding codes will also specify stimulation length, with a maximum of one hour (after which, stimulation will be turned off). Of note, stimulation also turns off if there is not good connectivity between the earpiece and the tragus (e.g., if the earpiece falls off or if it is placed on another part of the body without adequate connectivity).

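### No listed measure checks whether the tVNS versus sham blind holds, and staff blinding is not stated, so a self-report difference could include an expectancy component of unknown size

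*Combined protocol and SAP*

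**What the plan says.** The combined protocol and SAP describes the sham under Nerve Stimulation (Calibration and Blinding), after the Analysis Plan.

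- **Calibration.** Intensity is stepped up until the participant reports discomfort, with "a brief pause at each step during which the participant will be asked what the stimulus felt like to them". Then "The stimulation intensity will then be set to 80% of the discomfort threshold for the active tVNS group", and sham is set "near to 0% (just enough to keep device on) of the discomfort threshold for the sham stimulation group".
- **Masking of participants.** "Participants will be blinded to condition and told that, after calibration", the intensity will be below the discomfort level "and that they may not feel the stimulation once reduced". The plan calls this a psychological sham that the team has used before.
- **Codes.** Stimulation runs on single-use codes that carry the assigned settings: "Participants will be provided with a maximum of 14 blinding codes that correspond with the appropriate stimulation parameters and intensity depending on their group assignment". The text does not say who generates or holds them.
- **Consent script (section 6.2).** Stimulation participants are told that they will get one of two types of stimulation. They also hear "that we think one of the conditions may be more effective, and that they have a 50/50 chance of being in that group". In this account of the script, neither type is called sham.
- **Allocation and contact (section 6.2).** Active and sham are assigned in alternating order. A research assistant re-contacts a participant whose photograph shows poor electrode placement.
- **Measures and analysis (section 6.6 and Analysis Plan).** None of the listed scales asks for a treatment guess, confidence in it, or expected benefit. The models use time and group, with no blinding check.

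**The concern.** Hypotheses 4.1 and 4.2 predict that tVNS + mindfulness will do better than sham + mindfulness on sleep and mood. This is the contrast that isolates tVNS: in Table 1 the two arms differ only in the stimulation, whereas comparisons with the control group cross an assignment made on device availability. Many of the outcomes are self-rated (PSQI, ESS, PHQ-8, GAD-7, PSS, PANAS).

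Both arms learn at calibration what the stimulus feels like. They then have up to 14 home sessions in which to notice whether that feeling is present, knowing that one type is thought better. If sensation leads more active than sham participants to believe that they have the better type, and belief shifts ratings, the estimated effect contains that shift. Staff who know or can infer the arm could add to it in how they train and coach.

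Aim 4 exists to produce effect sizes, and section 5 says these will inform future trials. An unseen expectancy component would pass into that planning, and beliefs not asked for during the study cannot be reliably recovered afterwards.

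**Working it through.** **Step 1: check of the text.** Three questions, each answered from the documents.

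| Question | Finding |
|---|---|
| Do the arms differ in what could be felt at home? | 80% of threshold against near 0%. No perception threshold is given, so how many would feel 80% is unknown. |
| Who is declared blind? | Participants. Nothing is said about assistants, coordinator or analyst. |
| Is belief or expectancy recorded? | Not by any listed scale. AIM, IAM, FIM and SUS (week 4) cover acceptability, appropriateness, feasibility and usability. The wording of the open-ended questions is not given. |

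**Step 2: possible size.** The plan states no alpha, power, effect size or unblinding rate, so there is no figure of its own to reproduce. Only the 20 per arm (Table 1) comes from the documents.

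Bias in SD units = (share believing they have the better type in the active arm − the same share in the sham arm) × (effect of that belief on ratings).

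Standard error of a standardised difference at one time point = √(2/20) = 0.32 SD. A repeated-measures model may have a different standard error.

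With no true tVNS effect and an assumed two-sided alpha of 0.05, the chance of a significant result is Φ(bias/SE − 1.96) + Φ(−bias/SE − 1.96).

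| Belief gap (assumed) | Expectancy effect (assumed) | Bias | Bias/SE | Chance of p < 0.05 |
|---|---|---|---|---|
| 0 | any | 0 | 0 | 5.0% |
| 0.3 | 0.2 SD | 0.06 SD | 0.19 | 5.4% |
| 0.5 | 0.3 SD | 0.15 SD | 0.47 | 7.6% |
| 0.7 | 0.5 SD | 0.35 SD | 1.11 | 19.8% |

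**Step 3: what a guess item could show at 20 per arm.** The Bang index in an arm is 2p − 1, where p is the share guessing correctly and everyone guesses. At p = 0.5 its 95% half-width is 1.96 × 2 × √(0.25/20) = 0.44. An arm guessing at chance would thus be compatible with up to (1 + 0.44)/2 = 72% correct. For the difference between arms in the share guessing active, power is about 73% for 70% against 30% and about 92% for 80% against 30%. Only gross unblinding would show.

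**The case against.** The masking is more than one reassuring sentence. Both arms are told that they receive a type of stimulation, so feeling nothing does not clearly signal the lesser condition. The ramp, device, placement and codes are shared, and the team reports earlier use of this sham. All of that stands, although the documents report no blinding result from that use, and participants are also told that intensity will be reduced to a comfortable level, which some may take to mean something felt.

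A reader might go further and infer any of three things that the documents do not support:

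- **That the blind fails.** No data on sensation at 80%, or on guesses, are given.
- **That staff are unblinded.** The text is silent, and the codes may already hide the arm from some of them. Alternation does mean that anyone who knows one assignment can work out the next.
- **That the trial cannot separate tVNS from expectation on any outcome.** Fitbit sleep and overnight heart rate variability are less open to expectation, and hypothesis 4.1 covers sleep quantity as well as quality.

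Two further objections hold in part. The size is wholly assumed, and most of the range lies below one standard error. And this is a feasibility and effect-size study, not a confirmatory one; but that is the natural stage at which to learn whether the sham is credible.

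**Conclusion.** The point holds as a gap in measurement and reporting. Participant masking is planned but not verified, staff blinding is not stated, and a tVNS versus sham difference on self-report could include an expectancy component that the planned data cannot gauge.

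Under the assumed inputs that component is 0.06 to 0.35 SD, from negligible to slightly more than one standard error. The range rests on no figure in the documents apart from the 20 per arm. The concern is confined to self-rated outcomes in the tVNS versus sham contrast. It is worth acting on because the remedy is cheap and affects what the Aim 4 effect sizes can be said to show.

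**What to change.** 1. **Expectancy.** Add one item after calibration and before home use.
2. **Guess.** Add a treatment guess with confidence at the end of the existing week-1 survey. Stimulation is then still under way, and the PSQI, ESS, PHQ-8 and GAD-7 are not due until week 2. A guess taken only at week 2 would coincide with the end of stimulation and with those outcomes; repeating it then is optional. Report guesses by arm with a Bang index and its confidence interval, and state the limited precision at 20 per arm.
3. **Codes and allocation.** Have the coordinator issue the codes after receiving each calibrated threshold, and do not tell the arm to assistants who train, coach and follow up. Withholding codes is not enough while the order alternates, so replace alternation between tVNS and sham with a concealed random list held by the coordinator. Because the coordinator also places people in the stimulation stream, each line should be opened only after that placement. State who is blind.
4. **Interpretation.** State in advance that if guesses or expectancy clearly differ by arm, with what counts as clearly defined beforehand, self-report effect sizes will be described as possibly including expectation and shown beside the Fitbit results.

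**Cost.** A few survey items, and coordinator time around each calibration. Guesses can partly reflect benefit, and week-1 ratings such as the PSS and PANAS are taken in the same survey, so guesses need cautious reading. They flag a possible expectancy component but do not remove it. No change to stimulation settings is proposed.
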